### **5.4. Patient Registration**

Following appropriate pre-registration evaluation, a signed consent, HIPAA authorization, and completed eligibility checklist will be obtained (Appendix A). New patient registrations will be submitted to the clinical trials office by the study coordinator, who will record study data on all patients entered into the study and complete subsequent forms.

## 5.5. Study Procedures, Schedule of Events, Tracer Administration: Route and Dosing

### 5.5.1. Initial Visits Prior to PET Imaging

The patient will be under the care of their treating neuro-oncologist. The baseline measures of liver function, renal function, and electrolytes will be collected if not previously obtained within 28 days of the initial [F]FLT imaging visit. The following additional patient data will be obtained: histological diagnosis (when available following surgery), age at radiological diagnosis, gender, and other treatment modalities used. Clinical (non-research related) imaging studies, such as contrast MRI and/or standard clinical FDG PET, will be collected according to standard of care.

### 5.5.2. Multi-Tracer PET Exams

Multi-tracer PET exams of [F]FLT and [F]Fluciclovine will be acquired in each patient at up to three time points: (1) prior to any tumor-directed therapy, either prior to surgery or after surgery providing a complete surgical resection was not performed and confirmed by a post-operative contrast MRI scan where residual tumor  $\geq 1.0$  cm in diameter was present and prior to any tumor-directed therapy; (2) within 1-4 weeks after the conclusions of the initial (~6-8 weeks) chemoradiotherapy; and (3) patients with MRI-documented possible recurrence/progression versus treatment effect (pseudoprogression) within 6 months from the time of completion of chemoradiation. The abnormality must be  $\geq 1.0$  cm in diameter by contrast MRI or CT or show changes on non-enhancing MRI sequences (T2 or FLAIR).

Patients who were originally not enrolled to study baseline and conclusion of therapy imaging will be eligible to participate at the time of MRI-documented possible recurrence/progression versus treatment effect (pseudoprogression) within 6 months from the time of completion of chemoradiation. The abnormality must be  $\geq 1.0$  cm in diameter by contrast MRI or CT or show changes on non-enhancing MRI sequences (T2 or FLAIR).

### 5.5.3. Day of Research PET Scan(s)

The patient will have the appropriate IV access placed for radiotracer administration. The patient will then be positioned comfortably on the PET imaging table with the PET head-holder attachment. A CT scan for PET attenuation correction will be acquired using x-ray CT (PET/CT scanner). Dynamic PET scans of each tracer will then be acquired, which requires administration of the PET tracer(s) while the scanner is acquiring in dynamic mode. The details of tracer administration are summarized in Table 4.

Table 4. PET Tracer Administration: Route, Dosing, and Blood Sampling

Tracer	Route	Manner	Injected Dose	Scan Mode
[  F]FLT	IV	~60s push	~10 mCi	Dynamic
[  F]Fluciclovine	IV	~60s push	~10 mCi	Dynamic

Each radiotracer will be prepared by the investigational drug radiochemists in the PET cyclotron facility at HCI on the day of the scanning session. The tracer will be administered to the patient by a physician, nuclear medicine technologist, or trained research personnel in the PET imaging suite. Each tracer administration will be pushed by hand as a manually timed infusion (~60s) as indicated by Table 4, where each infusion is designed to optimize dynamic PET efficacy for that tracer.

Adverse events potentially related to the administration of [F]FLT or [F]Fluciclovine will be recorded at the conclusion of the [F]FLT or [F]Fluciclovine study. (Appendix B: Schedule of Events; Appendix D: [F]FLT Infusion Flow Chart, Appendix G: [F]Fluciclovine Infusion Flow Chart).

## 5.6. Data Collection

### 5.6.1. Safety Data Recorded During [F]FLT-PET and [F]Fluciclovine-PET Scans

Data collected on visit(s) for [F]FLT-PET and [F]Fluciclovine-PET scanning will be recorded on the [F]FLT or [F]Fluciclovine Protocol flow chart and will include: vital signs (including heart rate, blood pressure, and temperature) recorded just prior to the [F]FLT or [F]Fluciclovine infusion and then after the completion of the [F]FLT and [F]Fluciclovine imaging study. In addition to monitoring the above-mentioned safety parameters, an emergency code cart is located in the PET suite and can be utilized by the PET imaging team, as well as accessed by the code team at the institution should an emergent situation arise.

Additional information to be collected will include:

- Questioning of patient regarding adverse events immediately after each [F]FLT and [F]Fluciclovine administration.
- Patients may be discharged after the completion of the [F]FLT or [F]Fluciclovine imaging procedure if stable and if no adverse events are noted on questioning. Patients will be evaluated for adverse events after the completion of the [F]FLT and [F]Fluciclovine scans.

### 5.6.2. Tissue Collection and Analysis

All patients enrolled on this study will have undergone a neurosurgical procedure (either biopsy or tumor resection) in order to obtain a histological diagnosis of their tumors as part of standard care. Tissue specimens will be analyzed by the attending neuropathologist as part of routine care, who will assign a

histologic diagnosis and tumor grade according to World Health Organization (WHO) criteria. If sufficient tissue is available, specimens are routinely evaluated immunohistochemically for MIB-1, EGFR, p53, and IDH status; and by conventional light microscopy for vascularity. These results are routinely recorded on the surgical pathology report.

## 6. METHODS FOR EVALUATION OF IMAGING STUDIES

Each PET imaging study will be evaluated using qualitative, semi-quantitative, or fully-quantitative analysis techniques that have previously been used by us and other groups, and represent the standard and accepted means of evaluating static- and dynamic-PET images for these tracers. These assessments are described below for each tracer.

### 6.1. [F]FLT-PET Imaging

#### 6.1.1. [F]FLT Qualitative Visual Assessment

Qualitative (visual) assessment of level of uptake in brain tumor and normal brain will be performed. Regarding the initial question of tumor presence the following scale will be used: 1= definite tumor, 2 = probably tumor, 3 equivocal for tumor, 4 = probably not tumor, 5 = definitely not tumor. For the immediate post therapy imaging [F]FLT scan the same scales will be used. In the second group of patients where recurrence/progression (pseudoprogression) visual assessment on the [F]FLT-PET study will be interpreted as to confidence of tumor recurrence: 5 = definitely recurrence/progression, 4= probably recurrence/progression, 3= unable to differentiate recurrence/progression, 2= probably treatment effect/necrosis, 1= definitely treatment effect/necrosis.

#### 6.1.2. [F]FLT Semi-Quantitative Assessment

Semi-quantitative assessment of [F]FLT uptake will be performed by calculating  $SUV_{max}$  and  $SUV_{mean}$ . A region-of-interest (ROI) will be drawn over any tumor mass, necrotic region, or other abnormal region(s) on the summed static [F]FLT PET image. For each ROI, standardized uptake values (SUVs) with body surface-area correction will be obtained for both the maximum and mean voxel value in ROI:

$$SUV_{max} = \frac{A_{max}}{InjectedDose/BSA} \quad SUV_{mean} = \frac{A_{mean}}{InjectedDose/BSA}$$

$$BSA = W^{0.425} \times H^{0.725} \times 0.00718$$

$A_{max}$  = maximum voxel value in ROI ( $\mu$ Ci/mL; mCi/L; or MBq/L)

[figure not shown]
$A_{mean}$  = mean voxel value in ROI ( $\mu$ Ci/mL; mCi/L; or MBq/L)

$BSA$  = body surface area, computed from height H (cm) and weight W (kg)

Ratios of the SUV of tumor to that of white matter (T/WM) and cortex (T/C) will also be computed. The change in SUVs for pre-treatment (baseline) and post-treatment images will be computed and correlated with available histologic and clinical data.

### 6.1.3. [F]FLT Fully-Quantitative Assessment

Quantitative assessment of [F]FLT uptake will be performed by mathematical modeling of time activity curves for [F]FLT and its metabolites in blood and tissues. Several methods of analysis are being considered for evaluating [F]FLT images and results. A plausible scheme is outlined in the figure below.

The compartments describe the kinetic behavior of [F]FLT. Its transport across cell membranes is governed by two rate constants,  $K_1$  and  $k_2$ . The phosphorylation of [F]FLT is governed by the rate constant  $k_3$ . Evidence from FLT experiments in dogs suggests that [F]FLT is retained in cells without significant dephosphorylation ( $k_4$ ). We will initially assume that  $k_4$  is zero to simplify the modeling equations; the Akaike Information Criterion (AIC) will be used to determine if the time-activity curves support the more complex model ( $k_4 \neq 0$ ), which will then be used as indicated.

We will investigate the contribution of the labeled metabolite. If the labeled metabolite is restricted to the plasma space and urine and if the rate constant  $k_4$  is negligible, then the [F]FLT flux constant,  $K_{FLT}$  (mL/min/g), will be computed using graphical analysis (Patlak et al., 1983, Patlak and Blasberg, 1985). In the event that the [F]FLT metabolite contribution in tissue is significant, we will investigate the use of a metabolite-corrected flux constant as a measure of [F]FLT uptake (Mankoff et al., 1997, Muzi et al., 2005a, Muzi et al., 2005b, Shields et al., 2005, Muzi et al., 2006).

The parameters of interest for this model are those directly linked to DNA synthesis—specifically,  $k_3$  and  $K_{flux}$ , as they represent the phosphorylation of [F]FLT to reflect cellular proliferation. We will correlate these rates with proliferative (MIB-1) indices on histological tissue and S phase fraction determined by flow cytometry when these are available.

Procedure for [F]FLT plasma metabolite analyses: Dynamic arterial or heated hand blood sampling will be performed (Phelps et al., 1979). It is anticipated that the majority of patients will be assessed with the heated hand methodology thus eliminating the need for radial artery catheterization. Approximately 23 (1-2 mL) samples will be drawn over a period of 70 minutes with approximately 12 samples drawn in the first 2-3 minutes post injection and additional samples obtained at 4, 5, 7, 10, 15, 20, 30, 45, 60, and 70 minutes after injection. This sampling routine allows for determination of the whole blood and serum time activity curves. The whole blood samples will be counted and then centrifuged to separate plasma from cells. Aliquots of plasma (0.5 mL) will be counted for radioactivity. Another 0.5 mL of each plasma sample will be diluted with 3.5 mL of water and the resulting diluted plasma sample passed sequentially through a QMA cartridge followed by a C18 SepPak brand solid phase extraction cartridge. Then 4 mL of water will be passed sequentially through the cartridges to rinse them. The 8 mL of combined eluents will be counted to measure any [F] breakthrough. The QMA and C18 SepPaks will then be separated. [F]FLT glucuronide conjugate will be eluted from the QMA cartridge by passing 4 mL of 0.25M aqueous sodium citrate through the cartridge. [F]FLT will be eluted by passing 4 mL of ethanol through the C18 SepPak. All of the eluates will be counted for radioactivity. It should be noted that in certain individuals it is not possible to obtain adequate venous access to perform the dynamic blood sampling. In the event that adequate venous access is not possible, this analysis will not be required.

## 6.2. [F]Fluciclovine PET Imaging

### 6.2.1. [F]Fluciclovine Qualitative Visual Assessment

The uptake of [F]Fluciclovine is mediated by the sodium-independent “L” large-neutral amino acid transport (LAT) system. Since amino acid uptake is enhanced in malignancy, it accumulates faster and to a higher degree in cancer cells than normal cells, making it a promising biomarker for cancer diagnosis by PET imaging. Only a small fraction is excreted through the urinary pathway in the first hours after injection and it is not taken up to a high degree by normal brain tissue; therefore, unlike [F] fluorodeoxyglucose FDG, PET imaging with [F]Fluciclovine may be useful for the detection and diagnosis of prostate cancer and malignant gliomas. The ability of [F]Fluciclovine to detect malignant lesions in humans has been assessed in preliminary studies by the Emory group and others. [F]Fluciclovine is reported to have utility in the evaluation of primary and metastatic cancers in the brain, due to its low brain background uptake and high uptake by brain tumors (Shoup et al., 1999, Akhurst et al., 2006, Meirelles et al., 2006).

The following scale will be used to qualitatively assess tracer uptake in areas of abnormality, including tumor mass and necrotic regions, as related to normal brain regions: 1 = definite tumor, 2 = probably tumor, 3 equivocal for tumor, 4 = probably not tumor, 5 = definitely not tumor. In the second group of patients where recurrence/progression (pseudoprogression) visual assessment on the [F]Fluciclovine-PET study will be interpreted as to confidence of tumor recurrence: 5 = definitely recurrence/progression, 4 = probably recurrence/progression, 3 = unable to differentiate recurrence/progression, 2 = probably treatment effect/necrosis, 1 = definitely treatment effect/necrosis.

[figure not shown]
### 6.2.2. [F]Fluciclovine Semi-Quantitative Assessment

Semi-quantitative assessment of [F]Fluciclovine uptake will be performed by calculating  $SUV_{max}$  and  $SUV_{mean}$  in the same manner as for [F]FLT described earlier. SUVs will be calculated for summed static images from 70 minutes post injection. The change in SUVs for pre-treatment (baseline) and post-treatment images will be computed and correlated with available histologic and clinical data.

### 6.2.3. [F]Fluciclovine Fully-Quantitative Assessment

Fully-quantitative compartment modeling analysis of the dynamic [F]Fluciclovine-PET images will be performed according to the two-compartment model shown below, which has been previously described (Sasajima et al., 2013, Sørensen et al., 2013). As with the other tracers, parameters of interest include individual rate parameters ( $K_1$ ,  $k_2$ - $k_4$ ) and the net uptake parameters. The primary imaging endpoints for [F]Fluciclovine are not yet fully understood, and will in part be elucidated by this study. Of interest, the second-order retention ( $k_3$ ) and reversible ( $k_4$ ) parameters for this tracer have high potential for differentiating inflammatory processes occurring after radiotherapy from residual tumor activity.

Compartment modeling techniques will be applied to the dynamic PET data to obtain estimates of kinetic rate parameters ( $K_1$ ,  $k_2$ - $k_4$ ) and FDG net uptake ( $K_{net}$ ). Individual rate parameters will be computed using full compartment-modeling techniques according to the two-tissue compartment model shown below. Commercially available PET analysis software (e.g. PMOD Technologies LTD., Zurich, Switzerland) will be used. The net uptake parameter will be computed from both full compartment modeling and Patlak graphical analysis (Patlak et al., 1983, Patlak and Blasberg, 1985), both of which are standard and accepted methods.

Procedure for [F]Fluciclovine plasma analyses: Dynamic arterial or heated hand blood sampling will be performed (Phelps et al., 1979). It is anticipated that the majority of patients will be assessed with the heated hand methodology thus eliminating the need for radial artery catheterization. Approximately 23 (1-2 mL) samples will be drawn over a period of 70 minutes with approximately 12 samples drawn in the first 2-3 minutes post injection and additional samples obtained at 4, 5, 7, 10, 15, 20, 30, 45, 60, and 70 minutes after injection. This sampling routine allows for determination of the whole blood and serum time activity curves. The whole blood samples will be counted and then centrifuged to separate plasma from cells. Aliquots of plasma (0.5 mL) will be counted for radioactivity. It should be noted that in certain individuals it is not possible to obtain adequate venous access to perform the dynamic blood sampling. In the event that adequate venous access is not possible, this analysis will not be required.

### 6.3. Multi-Tracer Assessments in Conjunction

The exploratory aims of this study will assess the value of multi-tracer imaging endpoints, used in conjunction, over individual PET tracers for tumor characterization, predicting tumor aggressiveness, determination of functional changes that occur in response to therapy, and differentiating between recurrent/progressive tumor and treatment effect/necrosis (pseudoprogression). All three phases of image assessment will be studied: qualitative visual assessment (e.g. image scoring), semi-quantitative measures of tracer uptake (SUVs), and fully-quantitative measures ( $K_1$ - $k_4$ ;  $K_{net}$ ). In each case, combinations of imaging endpoints will be considered in conjunction, such as SUV ratios of tracer pairs, and compared with histologic measurements and clinical outcomes.

## 7. DATA ANALYSIS AND STATISTICS

### 7.1. Validation of Multi-Tracer PET Imaging Technology

This study will explore several hypotheses and provide preliminary exploratory data in the value of the two PET tracers [F]FLT and [F]Fluciclovine alone and in conjunction to assess response and differentiate tumor recurrence/progression from treatment effect/necrosis (pseudoprogression). The broader question of validating precisely what physiological quantity or process that each tracer/imaging endpoint measures and how these correlate with clinical endpoints and histologic data, when available, is the purpose of the study.

### 7.2 Data Analysis

*Qualitative and Visual Assessment.* The static images for each tracer will be visually assessed for any artifacts. The images will then be scored as described earlier for each tracer based on the level of uptake and confidence of tumor presence. Bland-Altman plots will be prepared.

*Semi- and Fully-Quantitative Assessments.*

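### The only analysis named for the 1-to-5 visual scores is a Bland-Altman plot, which does not suit five-category ordinal ratings; the pair compared is not stated.

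*Combined protocol and SAP*

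**What the plan says.** Section 7.2 gives the visual assessment three sentences. Static images are checked for artifacts. Then "The images will then be scored as described earlier for each tracer based on the level of uptake and confidence of tumor presence". Then "Bland-Altman plots will be prepared". It does not say what is plotted against what (two tracers, two readers, repeat reads or two sessions), how many readers score, or what limits would be acceptable.

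The scores are defined in 6.1.1 for FLT: "1= definite tumor, 2 = probably tumor, 3 equivocal for tumor, 4 = probably not tumor, 5 = definitely not tumor". Section 6.2.1 uses the same five categories for fluciclovine: "1 = definite tumor, 2 = probably tumor, 3 equivocal for tumor, 4 = probably not tumor, 5 = definitely not tumor". For suspected recurrence both sections turn the scale round, so that high numbers mean tumor: "5 = definitely recurrence/progression, 4= probably recurrence/progression".

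Section 6.3 makes visual scoring one of three kinds of assessment to be studied across tracers: "qualitative visual assessment (e.g. image scoring), semi-quantitative measures of tracer uptake (SUVs), and fully-quantitative measures". Combinations of imaging endpoints are to be "compared with histologic measurements and clinical outcomes", but no statistic is named for the scores.

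**The concern.** A Bland-Altman plot shows the difference of two measurements against their mean, with limits at the mean difference ± 1.96 SD. It is meant for roughly continuous differences, and it makes no allowance for agreement that would arise by chance. Differences between two 1-to-5 ratings are whole numbers from −4 to 4. If most ratings fall in one or two categories, the SD is small because there is little room to differ.

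Such clustering is plausible at baseline. The Group A inclusion criteria in 5.2 admit patients with strong imaging evidence of a high-grade tumor, an inoperable biopsied tumor, or an unresected or residual malignant tumor, and the question scored is whether tumor is present. Narrow limits might then be read as evidence that the two sets of scores carry the same information, when the plot cannot show that.

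**Working it through.** **Inputs.** The plan gives no figure for this analysis, so there is none to reproduce. The five ordered categories come from 6.1.1 and 6.2.1. The sample size of 22 is the number in 7.3 expected to have both tracers' scans after chemoradiotherapy. The score distributions are assumed and shown as a range.

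**Step 1: limits when the two scores are independent (kappa = 0 by construction).** If both scores have variance V, the SD of the difference is √(2V) and the limits are ±1.96 × √(2V). For two adjacent categories with a fraction p in the second, V = p(1 − p) and exact agreement is p² + (1 − p)².

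| Assumed distribution | V | SD of difference | Limits | Exact agreement | Kappa |
|---|---|---|---|---|---|
| 90/10 | 0.09 | √0.18 = 0.424 | ±0.83 | 82% | 0 |
| 85/15 | 0.1275 | √0.255 = 0.505 | ±0.99 | 74.5% | 0 |
| 75/25 | 0.1875 | √0.375 = 0.612 | ±1.20 | 62.5% | 0 |
| 70/20/10 | 2.4 − 1.4² = 0.44 | √0.88 = 0.938 | ±1.84 | 54% | 0 |
| uniform over 1–5 | 2 | √4 = 2 | ±3.92 | 20% | 0 |

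Agreement beyond chance is zero in every row, yet the width varies almost fivefold.

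**Step 2: nearly the same width from real agreement.** Let one score be uniform over the five categories, with 80% of pairs identical and 20% one category apart. Then SD = √0.20 = 0.447 and the limits are ±0.88. Chance agreement is 0.20, so kappa = (0.80 − 0.20)/(1 − 0.20) = 0.75. Limits of ±0.88 at kappa 0.75 cannot usefully be told from ±0.83 at kappa 0.

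**Step 3: the limits do not hold their nominal 95%.** Differences are whole numbers. Limits of ±0.83 or ±0.99 contain only a difference of 0, that is 82% or 74.5% of pairs. Limits of ±1.20 contain −1, 0 and +1, which is every possible pair when only two categories are used.

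**Step 4: range within one fixed distribution.** At 85/15, identical scores give ±0 and independent scores ±0.99. The worst case, in which no patient is in the second category on both, has 30% of pairs one apart: SD = √0.30 = 0.548, limits ±1.07, kappa = (0.70 − 0.745)/(1 − 0.745) = −0.18. The limits do respond to agreement, but they hardly separate chance from systematic discordance.

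**Step 5: what the plot looks like at n = 22.** In 20,000 simulated samples of independent 90/10 scores the median half-width was 0.84 (5th to 95th percentile 0.42 to 1.13). The plot typically had 3 distinct points. At 80/20 the half-width was 1.10 (0.77 to 1.38), with 4 points.

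**Step 6: scale direction.** A definite-tumor reading is 1 at the first two sessions and a definite-recurrence reading is 5 at the third. Compared across sessions without recoding, two consistent readings differ by |1 − 5| = 4.

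**Step 7: kappa at n = 22.** With 85/15 margins and an assumed true kappa of 0.6, simulated bootstrap 95% intervals have a median width close to 1.0 and include 0 in about three quarters of samples. At 90/10 with the same kappa, the chance that both scores of a patient fall in the first category is 0.81 + 0.6 × 0.09 = 0.864. The chance that at least one set of 22 scores is all in that category is then 2 × 0.90²² − 0.864²² = 15.7%. In those samples kappa is 0, or undefined if both sets are constant.

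**The case against.** The strongest reply has five parts.

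- **The pair is unknown.** A reader might infer that FLT is plotted against fluciclovine, since no second reader is named. Section 7.2 does not say so. This stands: the documented gap is that the pair is unspecified. The arithmetic is the same for any pair of ordinal scores.
- **Agreement between tracers is not an objective.** The tracers are chosen to measure different processes, and 6.3 sets their combined value against histology and outcome. This stands as well, so inter-tracer concordance should not be presented as a failed aim.
- **Clustering is assumed, and only baseline supports it.** No distribution is given, and after therapy or at suspected recurrence scores may well spread. A reader might infer that limits will be narrow whatever the true agreement; ±1.84 and ±3.92 at kappa 0 rule that out as a general claim.
- **Narrow limits are not false.** They correctly describe small absolute differences. At 85/15, 74.5% of pairs agree exactly and none differ by more than one category. It would be too strong to say the trial will report concordance that does not exist; the plot simply cannot separate it from chance.
- **The ROC analysis might take in the visual scores.** The recurrence rating is a natural ROC input, and the ROC bullet in 7.2 speaks of imaging markers generally. But it follows the heading for semi- and fully-quantitative assessments, and Table 3 lists only SUV and K parameters as PET biomarkers. Even on the generous reading it covers discrimination at suspected recurrence, not baseline or post-therapy scores or agreement between paired scores.

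**Conclusion.** The point holds in a limited form. The only analysis explicitly named for the visual scores is ill-suited to five-category ordinal ratings, and what it compares is not stated. The width of the limits reflects score spread: ±0.83 to ±1.20 at kappa 0 if scores fall 90/10 to 75/25 in two categories, and up to ±3.92 if they are uniform. The size of the problem rests on those assumed distributions; the mismatch between method and scale does not.

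The consequence is confined to exploratory, descriptive visual-score results. No test or decision rule in the plan depends on this plot, and the primary analysis of SUV reduction and overall survival is untouched. It should be corrected, but it does not threaten the trial's main result.

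**What to change.** In 7.2:

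1. State which pair of visual scores is compared: tracers, readers or repeat reads.
2. Replace the Bland-Altman plot of visual scores by the 5 × 5 cross-table for that pair, with exact and within-one-category agreement. Give it separately at each time point, because the scale direction reverses at the suspected-recurrence session.
3. Add linearly weighted kappa with a bootstrap 95% interval as a supplement only, and say that it may be imprecise or undefined if scores cluster.

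Bland-Altman plots can be kept for continuous pairs, such as the net uptake parameter from compartment modelling against that from Patlak graphical analysis (6.2.3).

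The cost is a sentence or two in 7.2. If the pair is the two tracers, no new data are needed; if it is readers or repeat reads, the plan must also provide for the second read. The downside is the weak precision of kappa at about 22 patients, which is why the cross-table comes first.
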